## List of Abbreviations

*Insert the abbreviation and definition for all abbreviations used throughout protocol.*

### Study Summary

Title	A prospective randomized controlled trial evaluating an accelerated 5 day pathway for discharge following pancreaticoduodenectomy (PD): Whipple Accelerated Recovery Pathway (WARP) trial
Short Title	Whipple Accelerated Recovery Pathway (WARP) trial
Protocol Number	
Phase	N/a
Methodology/Study Design	Randomized, controlled
Study Duration	3 years
Study Center(s)	Single-center
Objectives	The use of an accelerated pathway will result in a shorter postoperative hospital length of stay for patients undergoing PD without an increase in perioperative complications or readmission rates.
Number of Subjects	138
Diagnosis and Main Inclusion Criteria	Pancreatic cancer Inclusion: undergoing pancreaticoduodenectomy, firm gland texture
Study Therapy, Dose, Route, Regimen	N/A Study evaluating postoperative pathway with intensified physical therapy
Duration of administration and follow-up	N/A. Anticipated hospital stay 5-7 days, follow-up per routine postoperative follow up
Reference therapy	Comparison to be made to standard 7-day discharge pathway
Statistical Methodology	Two-sided alpha 0.05, power 80% to detect a increase in the proportion of patients discharged on POD 5 from 10% to 30%; 69 patients needed in each arm (138 total patients).
Schema	Pancreatic mass → eligible for resection → consent obtained → operative resection → randomization to 5 or 7 day discharge pathway → prospective collection of complications, length of stay, and cost data → phone calls to patients on first and second days after hospital discharge → standard routine outpatient follow-up afterwards.

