### **4.4 Subject Recruitment and Screening**

*138 adult patients will be recruited from the outpatient surgical clinics of the Pancreas, Biliary and Related Cancer Center. Investigators (surgeons) will offer enrollment at the time of consent for pancreaticoduodenectomy.*

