## 7.0 STATISTICAL PLAN

### 7.1 Sample Size Determination

The primary outcome is the proportion of patients discharged on postoperative day 5. Group sample sizes of 71 in group one (standard pathway) and 71 in group two (intervention arm) achieve 80% power to detect a difference between the group proportions of 0.20 (for patients discharged on postoperative day 5). The proportion in group two (intervention arm) is assumed to be 0.10 under the null hypothesis and 0.30 under the alternative hypothesis. The proportion in group one (the control group) is assumed to be 0.10 (the proportion in historical data is approximately 0.09). The test statistic used is the two-sided Fisher's Exact test. Power was calculated via simulation assuming an alpha of 0.05 spent between the interim and final analysis using an O'Brien-Fleming spending function as outlined below. In simulation of 100,000 trials, if the true rate in the intervention group is 0.30, the study stopped early for efficacy 16.2% of the time.

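### The Study Summary and section 4.4 set the trial at 138 patients, but section 7.1 needs 142 randomised; 138 fits a design with no interim look and gives 79.2% power under the planned boundaries

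*Combined protocol and SAP*

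**What the plan says.** The Study Summary gives the total as "Number of Subjects 138". Its statistical line reads "Two-sided alpha 0.05, power 80% to detect a increase in the proportion of patients discharged on POD 5 from 10% to 30" percent, with "69 patients needed in each arm (138 total patients" in all. It does not mention an interim analysis.

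Section 4.4 uses the same total at a different point in the patient's course: "138 adult patients will be recruited from the outpatient surgical clinics", with enrolment offered when consent for the operation is taken.

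Section 7.1 gives another size: "Group sample sizes of 71 in group one (standard pathway) and 71 in group two (intervention arm) achieve 80% power". That is 71 + 71 = 142. The assumptions are those of the summary. On the control arm: "The proportion in group one (the control group) is assumed to be 0.10". The intervention proportion is "assumed to be 0.10 under the null hypothesis and 0.30 under the alternative hypothesis". On the test: "The test statistic used is the two-sided Fisher's Exact test". Section 7.1 adds that alpha is spent over an interim and a final analysis, and that simulation gave a 16.2% chance of stopping early for efficacy when the true intervention rate is 0.30.

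Section 7.2 sets the interim at 72 patients, with stopping at p < 0.00506 and rejection at the final analysis at p < 0.04553. Its safety paragraph gives 36 per group at the interim. Section 7.3 expects length of stay to be complete for every patient.

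**The concern.** One comparison, with one set of rates, one alpha and one power, has two sample sizes. The four extra patients in section 7.1 cannot be a dropout allowance, because section 7.3 expects no missing primary data. The enrolment target decides when accrual closes. In an unblinded trial, two written targets leave room to stop at either one.

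The unit of counting also differs. Sections 1.3, 5.1 and 5.4 place randomisation at the end of the operation. Between clinic consent and randomisation come the firm-gland requirement (section 4.1) and the intraoperative exclusions (section 4.2: blood loss, failure to extubate, operative time, vascular resection). Some consented patients will never be randomised. If 138 is applied as section 4.4 words it, fewer than 138 reach the analysis.

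**Working it through.** **Inputs.** Control rate 0.10, intervention rate 0.30, two-sided Fisher's exact test, overall alpha 0.05 (section 7.1). Interim at 36 per arm with p < 0.00506; final with p < 0.04553 (section 7.2). Final size per arm n = 69 (Study Summary) or 71 (section 7.1).

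**Method.** All powers are exact sums over binomial outcomes, not simulations.

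- *Single look:* power(n) = Σ Bin(x; n, 0.10) · Bin(y; n, 0.30), summed over all pairs (x, y) whose Fisher p-value reaches significance at 0.05.
- *Two looks:* power(n) = P(p₁ < 0.00506 at 36 per arm) + P(p₁ ≥ 0.00506 and p₂ < 0.04553 at n per arm). The second term carries every non-stopping interim outcome forward and adds n − 36 further patients per arm.

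**Step 1: reproduce section 7.1.** With 71 per arm and two looks, early stopping has probability 0.163 and rejection at the final analysis 0.640, so power is 0.1632 + 0.6402 = 0.803. The plan states 16.2% and 80%. The calculation matches the plan.

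**Step 2: find the design that 69 per arm fits.** With a single look at alpha 0.05:

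| Per arm | Power |
|---|---|
| 68 | 79.97% |
| 69 | 80.73% |

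69 is where single-look power first reaches 80%. The summary's figure is therefore the Fisher sample size for a trial with no interim analysis.

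**Step 3: apply the planned boundaries to both sizes.**

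| Per arm | Total | Early stop | Reject at final | Power |
|---|---|---|---|---|
| 69 | 138 | 0.1632 | 0.6290 | 79.2% |
| 70 | 140 | 0.1632 | 0.6370 | 80.0% |
| 71 | 142 | 0.1632 | 0.6402 | 80.3% |

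At 138 randomised the shortfall is 80.0 − 79.2 = 0.8 points against the stated power, and 80.3 − 79.2 = 1.1 points against 142.

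**Step 4: read 138 as consented patients.** Let f be the share of consented patients who are randomised. The documents give no value, so f is an assumption shown over a range. The number randomised is 138·f, rounded down to equal arms, with the section 7.2 rule unchanged.

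| f (assumed) | 138·f | Randomised | Power |
|---|---|---|---|
| 0.8 | 110.4 | 110 (55 per arm) | 67.9% |
| 0.7 | 96.6 | 96 (48 per arm) | 59.6% |
| 0.6 | 82.8 | 82 (41 per arm) | 50.7% |

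**The case against.** The strongest reply is that the power loss is trivial. At 138 randomised it is under one point, and 70 per arm already reaches 80.0%, so 142 is the plan's stated number and not a strict minimum. Section 7.1 also puts the historical control proportion at about 0.09. At 0.09 v 0.30 the same two-look rule gives 84.4% with 69 per arm. All of this is correct, and it limits the size of the point. It does not remove it: 0.10 is the planning value in both places, and at that value the 80% claimed for 138 does not hold under the planned analysis.

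The second reply concerns the count. The summary speaks of patients in each arm, and a patient has an arm only after randomisation, so 138 there is a randomised count and section 4.4 may simply be loosely worded. Nothing says that accrual closes at 138 consents. This is a fair reading of the summary, and it makes the 51% to 68% figures conditional: they depend on section 4.4 being applied literally and on an assumed f. The wording of section 4.4 still permits that reading, and no other text rules it out.

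Third, the document does not say that the interim was added after 138 was set. The exact match with a single-look design, together with the summary's silence on an interim, is consistent with that history but does not establish it. Finally, the interim is fixed at 72 patients with numeric thresholds, so the early-stopping probability is the same for either final total. The change in information fraction (72/142 = 0.507 v 72/138 = 0.522) has no demonstrated effect on a decision, and the point does not rest on it.

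**Conclusion.** The point holds. The document carries two enrolment targets for one design, and the 80% power attached to 138 is not met under the section 7.2 boundaries. Taken as randomised patients, 138 costs 0.8 points of power, so this is mainly an inconsistency to correct and not a material loss. That figure rests on true rates of 0.10 and 0.30, equal arms, 36 per arm at the interim, and complete primary data. The more serious exposure is the undefined unit of counting: if 138 were enforced at clinic consent, power could fall well below 80%, by an amount that depends on a pass rate the documents do not give. Confidence is high on the mismatch and the 79.2%; the lower figures are scenarios only.

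**What to change.** State one target, counted at randomisation. In the Study Summary (number of subjects and statistical methodology) and in section 4.4, replace 138 with 142 randomised, 71 per arm, and mention the interim analysis in the summary's statistical line. In section 4.4, say that consent in clinic continues until 142 patients have been randomised after surgery, so that patients consented but excluded at operation do not count towards the target.

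If the sponsor prefers to keep 138 randomised, change section 7.1 to 69 per arm and restate the power there and in the summary as 79% under the section 7.2 thresholds.

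The first option costs wording in two places and four patients more than the summary gives, to which section 7.1 already commits. The second costs wording only. Under either option, more patients must be consented than randomised; section 4.4 could give an expected number if the site has data on how many pass the intraoperative criteria.

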## 1.0 INTRODUCTION

This document is a protocol for a human research study. This study is to be conducted according to US and international standards of Good Clinical Practice (FDA Title 21 part 312 and International Conference on Harmonization guidelines), applicable government regulations and Institutional research policies and procedures.

### 1.1 Specific Aims and Hypothesis

**Hypothesis:** The use of an accelerated pathway will result in a shorter postoperative hospital length of stay for patients undergoing PD without an increase in perioperative complications or readmission rates.

**Primary endpoint:** Post-operative length of stay (proportion of patients discharged by POD 5)

**Secondary endpoints:** Post-operative median length of stay, cost, readmission rate, post-operative complications (DGE, anastomotic leaks, intra-abdominal abscesses, wound infection, UTI, respiratory compromise, renal failure, etc.)

### 1.2 Background and Rationale

Standardization of post-operative care pathways has resulted in improved perioperative outcomes following complex abdominal operations. This has resulted in a shorter length of stay for many patients.

In pancreaticoduodenectomy specifically, the implementation of a post-operative pathway here at Jefferson has reduced the median length of stay to seven days and demonstrated that a fair proportion of patients (10%) leave the hospital in as early as five days. There are many reasons to encourage a shorter length of stay for these complex patients including: potential benefit to early mobilization and return to the home setting, decrease in hospital-acquired infectious complications, and of increasing importance in the modern setting, potential cost savings.

### 1.3 Study Therapy

1. Outpatient office: consent is obtained at the time of procedural consent during preoperative visit
2. Patients get standard preoperative, anesthetic, and operative protocols.
3. Randomization occurs at the end of the case when inclusion/exclusion criteria met.
4. The control arm follows the standard 7 day pathway
5. Care for the intervention arm is focused on seven specific interventions:
  - a. All patients are volume restricted in the perioperative period.
  - b. More rapidly leaving the ICU setting: Transfer from the ICU to floor directly following review of AM labs on POD 1

- c. More restful night sleep, 8 hour undisturbed period for patients recovering without apparent complication: routine lab draws starting POD 2 done at 6 am (rather than 1 am), midnight nursing rounds for vital signs are adjusted to 10 pm.
  - d. Early mobilization and enhanced physical therapy: formalized physical therapy protocol emphasizing early, frequent ambulation and mandated evaluation in the gym on POD 4 and 5. Physical therapy BID beginning POD 3 (may need adjustment to POD 4 or 5 pending PT staffing resource review)
  - e. Dietary modification: anticipated discharge with patients on 2/3rds liquid diet with dietary guidelines provided
  - f. Increased, and standardized, phone contact by nurse practitioner on first two days following hospital discharge.
6. Both groups: MO/RT referrals made on POD4, routine post-operative drain amylase studies POD 3, objective PT score for all patients on POD 5 (based on % of baseline timed get up and go), Attending survey to be completed POD 5 documenting readiness for discharge and rationale, discharge is at the discretion of the attending surgeon, routine drain amylase prior to removal to facilitate early decisions on drain removal v. anticipated discharge with drain in place.

#### **1.4 Preclinical Data**

In an informal review of our perioperative outcomes, we've found that nearly 10% of our patients at present leave the hospital five days following pancreaticoduodenectomy.

#### **1.5 Clinical Data to Date**

In an informal review of our perioperative outcomes, we've found that nearly 10% of our patients at present leave the hospital five days following pancreaticoduodenectomy.

#### **1.6 Dose Rationale and Risk/Benefits**

The major risks for this research are the development of postoperative complications in the outpatient setting, where identification of these complications may be delayed. The risk of fall due to early mobilization with physical therapy, and the potential for dehydration if patients are not able to tolerate adequate oral intake to maintain hydration at home following discharge. Specific measures to minimize these risks are detailed in the next question. Additional risks include violation of loss of confidentiality or violations in protecting personal health information.

The risk of a delayed diagnosis of postoperative complications will be mitigated with increased outpatient communication including daily phone calls and liberalized use of visiting nursing services and outpatient physical therapy. The risk of falls due to early mobilization will be mitigated by having physical therapy

and/or occupational therapy staff present at all additional therapy sessions beyond our current 7 day standard. The risk of dehydration will be mitigated by frequent daily phone contact by a highly-qualified nurse practitioner in the postoperative outpatient setting. Standard protocols as detailed above will be in place to protect patient PHI.

Patients in the study will benefit from increased and standardized physical and occupational therapy services in the postoperative setting, potential for improved pain control through the use of multimodal therapy, and increased preoperative and postoperative outpatient support by a highly-qualified service-specific nurse practitioner.

Decreased length of hospital stay and increased support (as detailed above) may prove to reduce the rate of overall complications and will allow patients return home quicker. Additional benefit may come in the form of reduced overall cost of care.

## **2.0 STUDY OBJECTIVES**

**Primary endpoint:** Post-operative length of stay (proportion of patients discharged by POD 5)

**Secondary endpoints:** Post-operative median length of stay, cost, readmission rate, post-operative complications (DGE, anastomotic leaks, intra-abdominal abscesses, wound infection, UTI, respiratory compromise, renal failure, etc.)

### **2.1 Primary Objective:**

The use of an accelerated pathway will result in a shorter postoperative hospital length of stay for patients undergoing PD without an increase in perioperative complications or readmission rates.

### **2.2 Secondary Objective:**

We anticipate lower cost, similar readmission rate, similar rate of post-operative complications (DGE, anastomotic leaks, intra-abdominal abscesses, wound infection, UTI, respiratory compromise, renal failure, etc.) in our study group

## **3.0 STUDY DESIGN**

### **3.1 General Design**

*Include:*

- *Randomized, controlled, non-blinded clinical trial*
- *Expected duration of subject participation: 5-7 days in hospital with study participation until their first postoperative visit*

### **3.2 Primary Study Endpoints**

**Primary endpoint:** Post-operative length of stay (proportion of patients discharged by POD 5)

### **3.3 Secondary Study Endpoints**

**Secondary endpoints:** Post-operative median length of stay, cost, readmission rate, post-operative complications (DGE, anastomotic leaks, intra-abdominal abscesses, wound infection, UTI, respiratory compromise, renal failure, etc.)

### **3.4 Primary Safety Endpoints**

*Perioperative complications, morbidity, mortality, and hospital readmission will all be tracked*

## **4.0 SUBJECT SELECTION AND WITHDRAWAL**

### **4.1 Inclusion Criteria**

**Inclusion criteria:** Pancreaticoduodenectomy, firm gland texture, subjects able to provide informed consent

### **4.2 Exclusion Criteria**

**Exclusion criteria:**

- Preoperative factors: CHF, ESRD, COPD, pregnancy, albumin < 3 gm/dL, poor preoperative performance status as defined by: timed get up and go (<15 seconds), patients cannot be homeless or have substance dependence
- Intraoperative factors: EBL > 1 liter, failure to extubate at the conclusion of the case, operative time > 8 hours, need for vascular resection/reconstruction

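### Section 4.2 defines poor performance status as a timed get up and go under 15 seconds, so read literally it excludes the fast patients and admits the slow ones

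*Combined protocol and SAP*

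**What the plan says.** Section 4.2 (Exclusion Criteria) lists, among the preoperative factors, "poor preoperative performance status as defined by: timed get up and go (<15 seconds"). The same list contains other numeric limits: "albumin < 3 gm/dL" among the preoperative factors and "EBL > 1 liter, failure to extubate at the conclusion of the case, operative time > 8 hours" among the intraoperative ones. The preoperative bullet ends with an item worded differently from the rest: "patients cannot be homeless or have substance dependence".

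The test appears again only in section 1.3 and its repeat in section 5.1, as a postoperative outcome measure: "objective PT score for all patients on POD 5 (based on % of baseline timed get up and go"). No threshold is given there. Neither the Study Summary nor section 4.1 (Inclusion Criteria) mentions the test.

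Eligibility is the gate to allocation. Section 1.3 states: "Randomization occurs at the end of the case when inclusion/exclusion criteria met".

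**The concern.** The criterion is meant to keep out patients whose mobility before surgery is poor. It then defines poor as finishing a timed mobility task quickly. The words and the number point in opposite directions, and the number is what a coordinator or auditor would check.

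What is at stake is who gets randomized:

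- **Population.** Followed literally, the rule lets through only patients at or above 15 seconds, the slow group that the label says should be kept out. Half of them would go to a pathway built on early and intensified mobilization. Section 1.6 names among the risks of the research "The risk of fall due to early mobilization with physical therapy".
- **Planning rates.** Section 7.1 assumes 0.10 discharged on day 5 under control and 0.30 under the intervention. The control figure comes from the center's own past patients (sections 1.2, 1.4, 1.5 and 7.1), and nothing says that they were restricted to slow performers. In a slow-only population both rates would lack support.
- **Conduct.** If staff instead follow the evident intent, each enrolled patient under 15 seconds breaches the written criterion. Section 10.2.1 has audits verify eligibility, and section 8.5.1 has the Medical Monitor review deviations. The wanted patients would then be recorded as eligibility violations.

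**Working it through.** No formula in the plan bears on this point, and there is no stated figure to reproduce. The check is a reading of the texts side by side.

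**1. Direction of the scale.** The measure is a time in seconds to complete a task. Lower is faster, and faster is better.

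**2. Convention of the list.** In section 4.2 each numeric limit gives the range that is excluded:

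| Item | Sign and limit | Excluded range | Is the excluded side the worse one? |
|---|---|---|---|
| Albumin | < 3 gm/dL | below 3 | yes |
| Blood loss | > 1 liter | above 1 | yes |
| Operative time | > 8 hours | above 8 | yes |
| Timed get up and go | < 15 seconds | below 15 | **no** |

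The other three signs all read sensibly, so a general corruption of inequality signs in the text is unlikely.

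**3. Literal application.** A time under 15 seconds is classed as poor and excluded. A time of 15 seconds or more is not excluded by this item. That is the reverse of the label.

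**4. Search for a correction elsewhere.** Sections 1.3 and 5.1 use the test only as a day 5 score relative to baseline, without a cut-off or direction. The Study Summary and section 4.1 are silent. Section 4.2 is therefore the only operative text.

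**5. Size.** The documents give no distribution of preoperative times, so the size can only be shown under an assumption. Let *p* be the share of candidates who finish in under 15 seconds.

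- Literal rule: share removed = *p*; share kept = 1 − *p*.
- Label's intent: share kept = *p* (leaving aside how exactly 15 seconds is handled).

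| Assumed *p* | Removed by literal rule | Kept by literal rule | Candidates per patient passing, literal: 1/(1 − *p*) | Same, by intent: 1/*p* |
|---|---|---|---|---|
| 0.70 | 70% | 30% | 1/0.30 = 3.3 | 1/0.70 = 1.4 |
| 0.95 | 95% | 5% | 1/0.05 = 20 | 1/0.95 = 1.05 |

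These figures concern this criterion alone. The contradiction does not depend on them.

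**6. Effect on the power calculation.** The arithmetic in section 7.1 is unchanged. What changes is whether its input rates describe the patients enrolled.

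**The case against.** The strongest reply is that nobody would apply the rule backwards. The excluded group is named in words, the trial is single-center, and the surgeons themselves offer enrollment (section 4.4). The parenthesis may have been meant as the pass mark a patient must reach. The item that follows it in the same bullet is also worded as a requirement inside an exclusion list, so mixed drafting is plausible.

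As an account of how the error arose, this is persuasive. As a defense of the text it fails, because the phrase introducing the number makes it the definition of poor, and every other limit in the list states the excluded range.

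Several limits do stand:

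- The documents do not show how the rule was applied, so actual mis-enrollment is not established.
- The range of 70% to 95% is an assumption, not evidence.
- Other exclusions still shape the population, so slow patients are admitted only as far as this criterion goes.
- Allocation follows eligibility, so both arms are affected alike. The threat is to the population studied, not to the validity of the comparison between arms.
- Section 1.6 offers mitigation for falls: therapy staff attend the additional sessions.
- A shift in the 10% and 30% rates is conceivable but not demonstrated.

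**Conclusion.** The concern holds. The only statement of the performance-status cut-off contradicts its own label, and nothing elsewhere in the document repairs it. On this criterion, literal use would classify every candidate the wrong way round, apart from the undefined case of exactly 15 seconds. How many patients that represents depends on a distribution the documents do not give.

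The conclusion rests on two things: that a shorter time is better performance, and that the parenthesis means what its introductory phrase says. It does not rest on any claim that patients were wrongly enrolled. Because the text gates randomization and can be read by staff, auditors and later readers in opposite ways, it must be fixed even though the intent is easy to guess.

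**What to change.** Amend section 4.2 so that the inequality agrees with the stated intent, that is, so that it points to the slow side of the cut-off and poor performers are the ones excluded. The sponsor should confirm the cut-off value and state how a time of exactly 15 seconds is handled.

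Make the same correction on the eligibility checklist or case report form. Check patients already screened against the corrected rule, recording any who were turned away or enrolled on the reversed reading.

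The cost is a one-character protocol amendment, a check of the screening form and a look back through any screening records. No extra patients or procedures are needed, and the sample-size calculation does not have to be redone on this account.
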